Appendix 2. CTCAE Grade for Laboratory Parameters

CTCAE 5.0	CTCAE Grade				
CTCAE Term	Grade 1	Grade 2	Grade 3	Grade 4	Grade 5
Anemia	Hemoglobin (Hgb) <LLN - 10.0 g/dL; <LLN - 6.2 mmol/L; <LLN - 100 g/L	Hgb <10.0 - 8.0 g/dL; <6.2 - 4.9 mmol/L; <100 - 80g/L	Hgb <8.0 g/dL; <4.9 mmol/L; <80 g/L; transfusion indicated	Life-threatening consequences; urgent intervention indicated	Death
Activated partial thromboplastin time prolonged	>ULN - 1.5 x ULN	>1.5 - 2.5 x ULN	>2.5 x ULN; bleeding	-	-
Alanine aminotransferase increased	>ULN - 3.0 x ULN if baseline was normal; 1.5 - 3.0 x baseline if baseline was abnormal	>3.0 - 5.0 x ULN if baseline was normal; >3.0 - 5.0 x baseline if baseline was abnormal	>5.0 - 20.0 x ULN if baseline was normal; >5.0 - 20.0 x baseline if baseline was abnormal	>20.0 x ULN if baseline was normal; >20.0 x baseline if baseline was abnormal	-
Alkaline phosphatase increased	>ULN - 2.5 x ULN if baseline was normal; 2.0 - 2.5 x baseline if baseline was abnormal	>2.5 - 5.0 x ULN if baseline was normal; >2.5 - 5.0 x baseline if baseline was abnormal	>5.0 - 20.0 x ULN if baseline was normal; >5.0 - 20.0 x baseline if baseline was abnormal	>20.0 x ULN if baseline was normal; >20.0 x baseline if baseline was abnormal	-
Aspartate aminotransferase increased	>ULN - 3.0 x ULN if baseline was normal; 1.5 - 3.0 x baseline if baseline was abnormal	>3.0 - 5.0 x ULN if baseline was normal; >3.0 - 5.0 x baseline if baseline was abnormal	>5.0 - 20.0 x ULN if baseline was normal; >5.0 - 20.0 x baseline if baseline was abnormal	>20.0 x ULN if baseline was normal; >20.0 x baseline if baseline was abnormal	-
Blood bicarbonate decreased	<LLN and no intervention initiated	-	-	-	-
Blood bilirubin increased	>ULN - 1.5 x ULN if baseline was normal; > 1.0 - 1.5 x baseline if baseline was abnormal	>1.5 - 3.0 x ULN if baseline was normal; >1.5 - 3.0 x baseline if baseline was abnormal	>3.0 - 10.0 x ULN if baseline was normal; >3.0 - 10.0 x baseline if baseline was abnormal	>10.0 x ULN if baseline was normal; >10.0 x baseline if baseline was abnormal	-
Cholesterol high	>ULN - 300 mg/dL; >ULN - 7.75 mmol/L	>300 - 400 mg/dL; >7.75 - 10.34 mmol/L	>400 - 500 mg/dL; >10.34 - 12.92 mmol/L	>500 mg/dL; >12.92 mmol/L	-
CPK increased	>ULN - 2.5 x ULN	>2.5 x ULN - 5 x ULN	>5 x ULN - 10 x ULN	>10 x ULN	-
Creatinine increased	>ULN - 1.5 x ULN	>1.5 - 3.0 x baseline; >1.5 - 3.0 x ULN	>3.0 x baseline; >3.0 - 6.0 x ULN	>6.0 x ULN	-

CTCAE 5.0	CTCAE Grade				
CTCAE Term	Grade 1	Grade 2	Grade 3	Grade 4	Grade 5
GGT increased	>ULN - 2.5 x ULN if baseline was normal; 2.0 - 2.5 x baseline if baseline was abnormal	>2.5 - 5.0 x ULN if baseline was normal; >2.5 - 5.0 x baseline if baseline was abnormal	>5.0 - 20.0 x ULN if baseline was normal; >5.0 - 20.0 x baseline if baseline was abnormal	>20.0 x ULN if baseline was normal; >20.0 x baseline if baseline was abnormal	-
Haptoglobin decreased	<LLN	-	-	-	-
Hemoglobin increased	Increase in >0 - 2 g/dL	Increase in >2 - 4 g/dL	Increase in >4 g/dL	-	-
INR increased	>1.2 - 1.5; >1 - 1.5 x baseline if on anticoagulation; monitoring only indicated	>1.5 - 2.5; >1.5 - 2.5 x baseline if on anticoagulation; dose adjustment indicated	>2.5; >2.5 x baseline if on anticoagulation; bleeding	-	-
Lipase increased	>ULN - 1.5 x ULN	>1.5 - 2.0 x ULN; >2.0 - 5.0 x ULN and asymptomatic	>2.0 - 5.0 x ULN with signs or symptoms; >5.0 x ULN and asymptomatic	>5.0 x ULN and with signs or symptoms	-
Lymphocyte count decreased	<LLN - 800/mm ³ ; <LLN - 0.8 x 10 ⁹ /L	<800 - 500/mm ³ ; <0.8 - 0.5 x 10 ⁹ /L	<500 - 200/mm ³ ; <0.5 - 0.2 x 10 ⁹ /L	<200/mm ³ ; <0.2 x 10 ⁹ /L	-
Lymphocyte count increased	-	>4000/mm ³ - 20,000/mm ³	>20,000/mm ³	-	-
Neutrophil count decreased	<LLN - 1500/mm ³ ; <LLN - 1.5 x 10 ⁹ /L	<1500 - 1000/mm ³ ; <1.5 - 1.0 x 10 ⁹ /L	<1000 - 500/mm ³ ; <1.0 - 0.5 x 10 ⁹ /L	<500/mm ³ ; <0.5 x 10 ⁹ /L	-
Platelet count decreased	<LLN - 75,000/mm ³ ; <LLN - 75.0 x 10 ⁹ /L	<75,000 - 50,000/mm ³ ; <75.0 - 50.0 x 10 ⁹ /L	<50,000 - 25,000/mm ³ ; <50.0 - 25.0 x 10 ⁹ /L	<25,000/mm ³ ; <25.0 x 10 ⁹ /L	-
Serum amylase increased	>ULN - 1.5 x ULN	>1.5 - 2.0 x ULN; >2.0 - 5.0 x ULN and asymptomatic	>2.0 - 5.0 x ULN with signs or symptoms; >5.0 x ULN and asymptomatic	>5.0 x ULN and with signs or symptoms	-
White blood cell decreased	<LLN - 3000/mm ³ ; <LLN - 3.0 x 10 ⁹ /L	<3000 - 2000/mm ³ ; <3.0 - 2.0 x 10 ⁹ /L	<2000 - 1000/mm ³ ; <2.0 - 1.0 x 10 ⁹ /L	<1000/mm ³ ; <1.0 x 10 ⁹ /L	-
Hypercalcemia	Corrected serum calcium of >ULN - 11.5 mg/dL; >ULN - 2.9 mmol/L; Ionized calcium >ULN - 1.5 mmol/L	Corrected serum calcium of >11.5 - 12.5 mg/dL; >2.9 - 3.1 mmol/L; Ionized calcium >1.5 - 1.6 mmol/L; symptomatic	Corrected serum calcium of >12.5 - 13.5 mg/dL; >3.1 - 3.4 mmol/L; Ionized calcium >1.6 - 1.8 mmol/L; hospitalization indicated	Corrected serum calcium of >13.5 mg/dL; >3.4 mmol/L; Ionized calcium >1.8 mmol/L; life-threatening consequences	Death

CTCAE 5.0		CTCAE Grade				
CTCAE Term	Grade 1	Grade 2	Grade 3	Grade 4	Grade 5	
Hyperkalemia	>ULN - 5.5 mmol/L	>5.5 - 6.0 mmol/L; intervention initiated	>6.0 - 7.0 mmol/L; hospitalization indicated	>7.0 mmol/L; life-threatening consequences	Death	
Hypermagnesemia	>ULN - 3.0 mg/dL; >ULN - 1.23 mmol/L	-	>3.0 - 8.0 mg/dL; >1.23 - 3.30 mmol/L	>8.0 mg/dL; >3.30 mmol/L; life-threatening consequences	Death	
Hypernatremia	>ULN - 150 mmol/L	>150 - 155 mmol/L; intervention initiated	>155 - 160 mmol/L; hospitalization indicated	>160 mmol/L; life-threatening consequences	Death	
Hypertriglyceridemia	150 mg/dL - 300 mg/dL; 1.71 mmol/L - 3.42 mmol/L	>300 mg/dL - 500 mg/dL; >3.42 mmol/L - 5.7 mmol/L	>500 mg/dL - 1000 mg/dL; >5.7 mmol/L - 11.4 mmol/L	>1000 mg/dL; >11.4 mmol/L; life-threatening consequences	Death	
Hyperuricemia	>ULN without physiologic consequences	-	>ULN with physiologic consequences	Life-threatening consequences	Death	
Hypoalbuminemia	<LLN - 3 g/dL; <LLN - 30 g/L	<3 - 2 g/dL; <30 - 20 g/L	<2 g/dL; <20 g/L	Life-threatening consequences; urgent intervention indicated	Death	
Hypocalcemia	Corrected serum calcium of <LLN - 8.0 mg/dL; <LLN - 2.0 mmol/L; Ionized calcium <LLN - 1.0 mmol/L	Corrected serum calcium of <8.0 - 7.0 mg/dL; <2.0 - 1.75 mmol/L; Ionized calcium <1.0 - 0.9 mmol/L; symptomatic	Corrected serum calcium of <7.0 - 6.0 mg/dL; <1.75 - 1.5 mmol/L; Ionized calcium <0.9 - 0.8 mmol/L; hospitalization indicated	Corrected serum calcium of <6.0 mg/dL; <1.5 mmol/L; Ionized calcium <0.8 mmol/L; life-threatening consequences	Death	
Hypoglycemia	<LLN - 55 mg/dL; <LLN - 3.0 mmol/L	<55 - 40 mg/dL; <3.0 - 2.2 mmol/L	<40 - 30 mg/dL; <2.2 - 1.7 mmol/L	<30 mg/dL; <1.7 mmol/L; life-threatening consequences; seizures	Death	
Hypokalemia	<LLN - 3.0 mmol/L	Symptomatic with <LLN - 3.0 mmol/L; intervention indicated	<3.0 - 2.5 mmol/L; hospitalization indicated	<2.5 mmol/L; life-threatening consequences	Death	
Hypomagnesemia	<LLN - 1.2 mg/dL; <LLN - 0.5 mmol/L	<1.2 - 0.9 mg/dL; <0.5 - 0.4 mmol/L	<0.9 - 0.7 mg/dL; <0.4 - 0.3 mmol/L	<0.7 mg/dL; <0.3 mmol/L; life-threatening consequences	Death	
Hyponatremia	<LLN - 130 mmol/L	125-129 mmol/L and asymptomatic	125-129 mmol/L symptomatic; 120-124 mmol/L regardless of symptoms	<120 mmol/L; life-threatening consequences	Death	

* Since anticoagulation medication is NOT captured in lab data, the condition for anticoagulation medication is ignored in the grade derivation.

Note: Refer to Common Terminology Criteria for Adverse Events (CTCAE) Version 5.0, which can be found at https://evs.nci.nih.gov/ftp1/CTCAE/CTCAE_5.0

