After the Screening Period, in-clinic study visits will occur at Baseline/Day 1 and at Weeks 1, 4, 8, and 12. At minimum, vital signs, symptom-driven physical examination (PE) including ascites and HE, safety laboratory tests, pruritus assessment (VAS and 5-Itch), review for active IBD, for subjects with history of IBD (as appropriate, see Section 6.8.6), and review of AEs and CMs will be performed at every in-clinic visit.

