6.8. Procedures and Specifications

6.8.1. Clinical Laboratory Analytes

Chemistry:

Alanine aminotransferase, AST, albumin, ALP, bicarbonate, blood urea nitrogen (BUN), calcium, chloride, creatinine, glucose, lactate dehydrogenase (LDH), magnesium, phosphorus, potassium, sodium, total and direct bilirubin, total protein, uric acid, GGT

eGFR:

eGFR is estimated by creatinine clearance calculated by the Cockcroft-Gault equation
{Cockcroft 1976}.

$$\text{Male: eGFR (mL/min)} = \frac{[140 - \text{age (years)}] \times \text{BW(kg)}}{72 \times \text{S}_{\text{cr}}}$$

$$\text{Female: eGFR(mL/min)} = \frac{[140 - \text{age (years)}] \times \text{BW(kg)} \times 0.85}{72 \times \text{S}_{\text{cr}}}$$

BW body weight; S_{cr} serum creatinine (mg/dL)

Actual body weight will be used for the eGFR.

Hematology:

Hematocrit, hemoglobin (Hb), platelet count, red blood cell count (RBC), white blood cell count (WBC) with differential (absolute and percentage) including lymphocytes, monocytes, neutrophils, eosinophils, basophils, and reticulocyte count and mean corpuscular volume.

Coagulation Panel:

Prothrombin time, partial thromboplastin time (PTT), and INR.

Pregnancy Tests:

Serum beta human chorionic gonadotropin (β -hCG) or urine β -hCG (if positive, requires immediate confirmation with serum β -hCG), and serum FSH.

Additional Tests:

C-peptide, insulin and HbA_{1c}, Lipid Profile, HIV-1 (reflex to HIV-1 RNA), HBV (HBsAg) and HCV (reflex to HCV RNA) serology, eGFR as calculated by modification of diet in renal disease (MDRD), urine drug screen (for amphetamines, cocaine, opiates), stool collection (if available), genomic sample collection, and creatine phosphokinase (CPK) testing (for Close Observation as needed per Section 7.5.2).

Biomarker tests:

- Inflammation high sensitivity C-reactive protein (hsCRP)

[REDACTED]

[REDACTED]

[REDACTED]

[REDACTED]

CCI

[REDACTED]

[REDACTED]

[REDACTED]

[REDACTED]

[REDACTED]

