Data relating to unscheduled visits may be assigned to a particular visit or time point based on the visit windows. The following conventions will be followed:

- An unscheduled visit prior to the first dosing of study drug may be included in the calculation of the baseline value, if applicable.
- Unscheduled visits after the first dose of study drug will be included in determining the maximum postbaseline toxicity grade.
- For subjects who prematurely discontinue from the study, early termination (ET) data will be summarized as a separate visit, labeled as “Early Termination Visit.”
- Data collected on a follow-up visit will be summarized as a separate visit and labeled “Follow-up Visit.”
- Data obtained after the follow-up visit or last dose date plus 30 days (whichever is later) will be excluded from the summaries but will be included in the listings.

3.7.3. Selection of Data in the Event of Multiple Records in an Analysis Visit Window

Depending on the statistical analysis method, single values may be required for each analysis window. For example, change from baseline by visit usually requires a single value, whereas a time-to-event analysis would not require 1 value per analysis window.

If multiple valid, nonmissing measurements exist in an analysis window, records will be chosen based on the following rules if a single value is needed:

- For baseline, the last nonmissing value on or prior to the first dosing date of study drug will be selected, unless specified differently. If there are multiple records with the same time or no time recorded on the same day, the baseline value will be the average of the measurements for continuous data, or the measurement with the lowest severity for categorical data.

- For each liver test (ALP, total bilirubin, ALT, AST, and GGT), the baseline value will be determined by averaging all values obtained between Screening and Baseline/Day 1 (inclusive). The corresponding baseline reference range will be defined as the one associated with the latest visit that was included for computing the baseline value, for the purpose of determination of the abnormality and/or toxicity grades.
- For postbaseline values:
 - The record closest to the nominal day for that visit will be selected.
 - If there are 2 or more records that are equidistant from the nominal day, the later record will be selected.

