7.2.2. Graded Laboratory Values

The CTCAE Version 5.0 will be used to assign toxicity grades (0 to 4) to laboratory results for analysis. Grade 0 includes all values that do not meet the criteria for an abnormality of at least Grade 1. For laboratory tests with criteria for both increased and decreased levels, analyses for each direction (ie, increased, decreased) will be presented separately.

For the baseline ALP, total bilirubin, GGT, ALT and AST toxicity grades, the CTCAE version 5.0 will be used to assign grades to the derived average values.

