7.2.2.1. Treatment-Emergent Laboratory Abnormalities

Treatment-emergent laboratory abnormalities are defined as values that increase at least 1 toxicity grade from baseline at any postbaseline time point, up to and including the date of last dose of study drug plus 30 days. If the relevant baseline laboratory value is missing, any abnormality of at least Grade 1 observed within the time frame specified above will be considered treatment emergent.

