7.2.2.2. Summaries of Laboratory Abnormalities

Laboratory data that are categorical will be summarized using the number and percentage of subjects in the study with the given response at baseline and each scheduled postbaseline visit.

The following summaries (number and percentage of subjects) for treatment-emergent laboratory abnormalities will be provided by lab test; subjects will be categorized according to the most severe postbaseline abnormality grade for a given lab test:

- Graded laboratory abnormalities

For all summaries of laboratory abnormalities, the denominator is the number of subjects with nonmissing postbaseline values up to 30 days after last dosing date.

A by-subject listing of treatment-emergent Grade 3 or 4 laboratory abnormalities will be provided by subject ID number and visit in chronological order. This listing will include all test results that were collected throughout the study for the lab test of interest, with all applicable severity grades or abnormal flags displayed.

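### SAP Appendix 2 grades any rise in hemoglobin as Grade 1 with no upper-limit condition, so most fully followed subjects would enter that row by chance alone

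*SAP*

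**What the plan says.** - **Grading row.** SAP Appendix 2, Hemoglobin increased: Grade 1 is "Increase in >0 - 2 g/dL", Grade 2 is a rise of more than 2 and up to 4 g/dL, and Grade 3 a rise of more than 4 g/dL. The row has no ULN or abnormal-baseline condition and does not say what the increase is measured from. The table's footnote changes the derivation only for anticoagulation.
- **Grade 0.** SAP 7.2.2: "Grade 0 includes all values that do not meet the criteria for an abnormality of at least Grade 1".
- **Treatment-emergent.** SAP 7.2.2.1: "values that increase at least 1 toxicity grade from baseline at any postbaseline time point", up to the last dose plus 30 days.
- **Counting.** SAP 7.2.2.2: "subjects will be categorized according to the most severe postbaseline abnormality grade for a given lab test".
- **Baseline.** SAP 3.7.3: "For baseline, the last nonmissing value on or prior to the first dosing date of study drug will be selected, unless specified differently". Averaging of screening and Day 1 values applies to five liver tests only, so baseline hemoglobin is normally one value.
- **Sampling.** Protocol 6.8.1 puts hemoglobin in the hematology panel ("Hematocrit, hemoglobin (Hb), platelet count"). Protocol 6.2.1 states that "in-clinic study visits will occur at Baseline/Day 1 and at Weeks 1, 4, 8, and 12", and protocol 6.4.4 adds a follow-up sample. Under SAP 3.7.2, unscheduled samples after the first dose also count toward the worst grade.

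**The concern.** A value cannot exceed itself, so the baseline value is Grade 0 on this row by construction. Any later value that is higher, by however little, is then one grade worse and treatment-emergent. A subject who moves from 13.0 to 13.1 g/dL, both assumed normal, is counted. So is an anemic subject who recovers from 10.0 to 10.4 g/dL. If 10.4 is still below the lower limit of normal, that one sample would carry both Grade 1 Anemia and a treatment-emergent Grade 1 Hemoglobin increased.

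Clinical laboratory tests are a named component of the primary safety endpoint (protocol 8.1.2). SAP 7.2.1 drops descriptive statistics for laboratory tests, so the graded table is the only tabulated summary of hemoglobin. There is no control group to show the background rate. A high percentage on this row could therefore be taken for a drug effect when it is mostly measurement and biological variation.

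**Working it through.** The plan states no expected rate, so there is no figure of its own to reproduce.

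**Step 1: other rows in Appendix 2.** Lipase, amylase, CPK and aPTT start at the ULN. Triglycerides and INR use absolute cut-offs. Bilirubin counts any rise above baseline, but only when baseline was abnormal. Creatinine has a baseline multiple without a ULN condition, but it requires more than 1.5 times baseline. Hemoglobin is the only row on which an arbitrarily small rise between two normal values earns a grade.

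**Step 2: number of postbaseline values, k.** Weeks 1, 4, 8 and 12 give k = 4. The follow-up visit is 28 ± 5 days after Week 12, that is 23 to 33 days, so it usually but not always falls within the last dose plus 30 days. When it does, k = 5.

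**Step 3: chance of being counted with no true change.** If the baseline and the k later values are exchangeable and untied, baseline is the highest of the k + 1 values with probability 1/(k + 1). Hence

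P(at least one value above baseline) = 1 − 1/(k + 1) = k/(k + 1).

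- k = 1: 1/2 = 50%
- k = 4: 4/5 = 80%
- k = 5: 5/6 = 83.3%

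**Step 4: rounding.** Ties lower these rates. The documents give neither the reporting precision nor the within-subject SD. Assuming results to 0.1 g/dL and independent values, simulation with 300,000 subjects per scenario gives:

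| Within-subject SD (g/dL) | k = 4 | k = 5 |
|---|---|---|
| 0.2 | 73.5% | 77.3% |
| 0.3 | 75.9% | 79.4% |
| 0.4 | 76.8% | 80.6% |
| 0.5 | 77.6% | 81.2% |
| 0.7 | 78.3% | 81.8% |

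A subject with one postbaseline sample is counted 43% to 48% of the time.

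**Step 5: serial correlation.** With SD 0.4 g/dL and the same rounding:

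| Correlation over 4 weeks | k = 4 | k = 5 |
|---|---|---|
| 0.3 | 77.6% | 81.3% |
| 0.5 | 76.1% | 79.8% |
| 0.7 | 73.4% | 77.1% |
| 0.9 | 66.8% | 71.0% |

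SD and correlation were varied separately. A small SD combined with strong correlation would give a lower rate than any shown.

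**Step 6: true shifts** (SD 0.4, k = 4, independent values). A sustained fall of 0.3 g/dL gives about 55%, a fall of 0.5 about 39%, and a rise of 0.3 about 91%. Even a real fall would leave many subjects on the increased row.

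**Step 7: higher grades.** Noise produces a rise of more than 2 g/dL in under 1% of subjects for SD up to 0.5, and in about 6% to 7% at SD 0.7. The inflation is essentially a Grade 1 matter.

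**Step 8: with a ULN condition** (illustration only). Assume within-subject SD 0.4, between-subject SD 1.4, mean 13.5 to 14 and ULN 16 to 17 g/dL. With k = 4, noise then flags about 1% to 10% of subjects, against about 77% under the printed rule.

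**The case against.** The strongest counter-argument is that the rule actually applied may not be the bare row. Protocol 8.5.3 assigns grading for analysis to the central laboratory. SAP Appendix 3 (Programming Specifications) is listed but was not available for this review. Either could supply a ULN condition or define the reference value. If the increase were measured above the ULN, the problem would disappear. This stands as a caveat, but Appendix 2 as printed does not say so, and two programmers could produce very different tables from it.

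The row may also simply transcribe CTCAE 5.0, which both documents specify. That cannot be checked from the documents and would not change the arithmetic. It does mean that a ULN condition is a sponsor adaptation rather than the correction of a slip.

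Three stronger readings are tempting, and the documents do not support them.

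- *True signals in other tests would be hidden.* SAP 7.2.2.2 tabulates by laboratory test and SAP 7.2.2 presents each direction separately, so the Anemia row and all other rows are untouched. The Grade 3 or 4 listing needs a rise of more than 4 g/dL on this row and is essentially unaffected.
- *The graded table is the only laboratory summary left.* SAP 7.2.3 keeps a separate table of ALT/AST, bilirubin and INR criteria. By-subject listings of hematology results also remain (SAP 7.2).
- *About 16 of the 20 planned subjects would be counted.* SAP 1 reports that enrollment was stopped early. The final number is not given, so only a proportion can be stated.

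Finally, the study has one arm and no formal testing (SAP 3.4), so no comparison is distorted. That limits the harm to how the safety table is read.

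**Conclusion.** The rule as printed gives a wrong result. If the increase is measured from baseline, about four in five fully followed subjects would be counted with a treatment-emergent Grade 1 hemoglobin increase when nothing has changed: 80% with the four on-treatment visits and 83% with follow-up. Allowing for rounding and serial correlation, the scenarios examined span about 67% to 83%. These rest on assumed reporting to 0.1 g/dL, within-subject SD of 0.2 to 0.7 g/dL and four-week correlation of 0 to 0.9. The rate is lower for subjects with few samples or a true fall, and higher with extra unscheduled samples or a true rise.

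The consequence is narrow: one row of the graded table, unneeded flags in the by-subject listings, and any total that pools all tests and grades (the SAP does not name one separately). It should be corrected because it sits within the primary safety endpoint and the data needed are already collected. It does not threaten the study's overall safety assessment.

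**What to change.** In SAP Appendix 2, assign Hemoglobin increased grades only to values above the ULN. Measure the increase above the ULN, or above baseline when baseline exceeds the ULN. Treat values at or below the ULN as Grade 0. Apply the same rule in the grading program, and confirm that the central laboratory's grading under protocol 8.5.3 follows it.

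Add a table footnote, as is already done for anticoagulation, and record the change in SAP 2.3. If the SAP has already been finalized, SAP 1 requires later changes to be documented in the clinical study report.

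The cost is one line in the appendix and one in the program, with no new data. The small downside is a documented sponsor departure from the printed CTCAE 5.0 criterion, so this row would no longer be directly comparable with studies that apply that criterion as printed.
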